Robbin et al 2006 (18)	126	
 • Duplex Scan (Ultrasound) 	AVG	AVG Survival	Not beneficial
Tessitore et al. 2004	79	
 • Access flow 	AVF	Thrombosis	Beneficial

Study Design

Randomized, Prospective Clinical Trial. Patients, PI, funder (Transonic) and statistician blinded (this will be implemented in Velos). Intervention and standard of care are different and cannot be blinded from attending nurses or clinic personnel. If a patient needs to switch schedules, they need to switch to shift that matches their protocol. Otherwise, they will need to switch protocols. No Transonic (funding) personnel will be involved in study design, protocol, analysis, or publication.

Randomization:

Patient is consented, baseline assessment taken, and evaluated for inclusion before randomization (baseline data will be included in analysis to determine representativeness of study patients to clinic patients). Randomization will occur after enrollment period ends.

The intervention and control protocols are significantly different that individual patients in the same dialysis session would be able to identify which arm they are in. Therefore, blocks of patients will be randomized according to dialysis schedule within each clinic.

Hemodialysis Access Surveillance Evaluation (HASE) Study

Because the staffing is similar across shifts, we will do block randomization where all patients in a shift are assigned to the same protocol at each clinic site. For each clinic, the blocks will be given a number based on chronological order (Monday 1st shift = 1, Monday 2nd shift = 2 +, Monday 3rd shift = 3, Tuesday 1st shift = 4, Tuesday 2nd shift = 5, Tuesday 3rd shift = 6). For each clinic site, a coin will be flipped in front of two witnesses: heads = first group treatment; tails = first group control. Then a die will be rolled. The number that is rolled will the first group assigned (based on coin toss). The remaining groups will be allocated in sequence. For instance, if the coin lands on heads and the die lands on 3, Monday 3rd shift is intervention, Tuesday 1st shift is control, Tuesday 2nd shift is intervention, Tuesday 3rd shift if control, Monday 1st shift is intervention and Monday 2nd shift is control. If a patient has to switch dialysis schedules, care must be taken to place them in the same arm.

Inclusion and Exclusion Criteria

Inclusion criteria:

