Chronic hemodialysis patients undergoing dialysis therapy via an upper extremity arteriovenous access (arteriovenous fistula or an arteriovenous graft) will be enrolled to have monthly surveillance flow measurement using Transonic system or physical examination of the arteriovenous access by qualified person at least once a month for a period of 2 years.

Exclusion criteria:

- Patients requiring surgical intervention on the arteriovenous access.
- History of access thrombosis (one or more access thrombosis of the current AV access).
- Patients with signs of access infection.
- Patients with a malignancy.
- Patients with life expectancy of less than six months.
- Unable to understand the study.
- Unable to sign the consent form.
- Patients with psychiatric disorder.
- Age less than 18 or greater than 80 years.
- Adults unable to consent
- Individuals who are not yet adults (infants, children, teenagers)
- Pregnant women
- Prisoners

Procedures Involved

Chronic hemodialysis patients receiving treatment with an upper extremity arteriovenous access will be enrolled in this 2 year study. End of study starts as last patient from 450 completes follow-up. Patients would be randomly assigned into surveillance or the control group. Randomization will take a cluster pattern per shift. (shift randomization).

Hemodialysis Access Surveillance Evaluation (HASE) Study

Surveillance group

- a. Surveillance group would receive monthly blood flow surveillance by ultrasound dilution technique (using the Transonic system) plus standard care (see below). Patients would be referred for an intervention based on the current KDOQI recommendations i.e. access flow of less than 600 ml/minute for arteriovenous grafts and less than 500 ml/minute for patients with arteriovenous fistulas or if the access flow is 1000 ml/minute that has decreased by more than 25% over 4 months (1). In addition to the detection of access dysfunction, the time interval between the detection of access dysfunction by the Transonic system and the intervention will also be recorded.

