- b. Patients will be referred for an intervention if clinical indication is met. Clinical indications include prolonged bleeding for more than 30 minutes (cannot be explained by medication), upper extremity edema, difficult cannulation, aspiration of clots during cannulation, aneurysmal formation. Access pressure that prevents normal HD machine operation (such as high venous pressure [>250 mm Hg] on three or more consecutive dialysis treatments, negative arterial pressure [<-250 mm hg] on three or more consecutive dialysis treatments). Any Kt/V that cannot be explained by other factors and high recirculation rate of more than 10% would be checked by Transonic Recirculation/flow test prior to referral (rear event).

Control group

Control group will receive standard monitoring (standard care). Standard monitoring is physical examination by a qualified individual (nurse) at each dialysis encounter. Patients will be referred for an intervention if clinical indication is met. Clinical indications include prolonged bleeding for more than 30 minutes, low Kt/v that cannot be explained by other factors, high venous pressure (>250 mm hg) on three or more consecutive dialysis treatments, negative arterial pressure (<-250 mm hg) on three or more consecutive dialysis treatments, upper extremity edema, difficulty cannulation, aspiration of clots during cannulation, aneurysmal formation and high recirculation of more than 10%.

Enrollment period

Enrollment period is expected to be 3-6 months.

Transonic measurement protocol:

Access recirculation, access flow would be determined using the ultrasound dilution technique (Transonic system).

1. Within 90 min of the beginning of HD session HD03 sensors are clamped HD tubing lines
2. Recirculation, access flow will be performed according to HD03 Manual.
3. Post intervention evaluation is as per each arm follow up unless other follow up deemed necessary by the interventionalist.

Hemodialysis Access Surveillance Evaluation (HASE) Study

Data Management

Primary Hypothesis:

H_0 : Patients screened monthly with Transonic Ultrasound Dilution Technique (UDT) and followed up with proactive intervention (if clinically indicated) will not have a rate of access thrombosis that is different than patients receiving physical examination and reactive intervention (if clinically indicated).

Secondary Hypotheses:

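### The bleeding trigger for referral differs between arms, although surveillance is defined as flow measurement added to standard care

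*Combined protocol and SAP*

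**What the plan says.** All references are to the combined protocol and SAP. Under Procedures Involved, Surveillance group item a, the surveillance arm receives monthly ultrasound dilution flow measurement "plus standard care (see below"). The next subsection states: "Control group will receive standard monitoring (standard care"). Standard care is thus the common base, and flow measurement is the stated addition.

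Each arm then has its own list of clinical indications for referral. Surveillance group item b includes "prolonged bleeding for more than 30 minutes (cannot be explained by medication"). The Control group list opens: "Clinical indications include prolonged bleeding for more than 30 minutes, low Kt/v that cannot be explained by other factors". The control bleeding trigger carries no medication exception, and no other section extends the exception to controls.

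The lists also differ in wording elsewhere. Under surveillance, unexplained Kt/V and "high recirculation rate of more than 10% would be checked by Transonic Recirculation/flow test prior to referral", and the text marks this as a rare event (misspelled). The pressure limits under surveillance are introduced as examples: "Access pressure that prevents normal HD machine operation (such as high venous pressure".

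**The concern.** In a trial of an added test, everything except the test and what follows from it should be the same in both arms. Here the rule for acting on one clinical sign depends on the arm. The people applying it know the arm, since Study Design says: "Intervention and standard of care are different and cannot be blinded from attending nurses or clinic personnel". Randomization is by shift within a clinic, and the protocol describes staffing as alike across shifts. Similar staff are therefore asked to use one bleeding rule on some shifts and another on the rest.

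At stake is the meaning of the arm comparison for outcomes that depend on referral. The most direct is the number of angioplasties (H0-2). If control patients are sent for angiogram because of medication-explained bleeding and surveillance patients are not, part of any difference in procedures reflects the bleeding rule rather than flow surveillance.

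**Working it through.** The protocol attaches no figure to this point, so the check sets the two lists side by side, taking the nine control triggers in turn.

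| Control trigger | Surveillance item b | Comparison |
|---|---|---|
| Bleeding over 30 minutes | Same duration, but not if explained by medication | Different rule |
| Low, unexplained Kt/V | Unexplained Kt/V, Transonic check first | Open |
| Recirculation above 10% | Same limit, Transonic check first | Open |
| High venous pressure | Same limit and number of treatments, given as an example | Same limit |
| Negative arterial pressure | Same limit and number of treatments, given as an example | Same limit |
| Arm edema | Same | Same |
| Difficult cannulation | Same | Same |
| Clots on cannulation | Same | Same |
| Aneurysm | Same | Same |

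Count: 1 different + 2 open + 2 with the same limits + 4 the same = 9. The count says nothing about how often each trigger occurs.

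**Bleeding.** Take a patient who bleeds for more than 30 minutes, where medication explains it and no other sign is present. On a control shift the trigger is met and the text says that patients who meet an indication will be referred. On a surveillance shift the listed trigger is not met. The parenthesis has no function unless it excludes some bleeding.

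**Kt/V and recirculation.** Testing first and then referring satisfies both lists. They diverge only if a normal test cancels the referral, and the protocol does not say whether it does. The measurement section is not limited to one arm: "Access recirculation, access flow would be determined using the ultrasound dilution technique (Transonic system"). A control patient's recirculation may therefore also be a Transonic result.

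**Size.** For the bleeding rule alone, followed literally:

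extra control angioplasties = N × r × a

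Here N is the number of medication-explained episodes over 30 minutes among controls, r is the fraction referred for that reason only, and a is the fraction of those referrals that end in angioplasty. The documents give none of the three. Since r and a each lie between 0 and 1, the result lies between 0 and N, and N is unknown. The sign is fixed for this component: it can only add control procedures relative to surveillance.

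**Adjustment.** Step 5 of the Statistical Analysis adjusts for nurse, center and city. The protocol does not claim that this handles referral rules, and it could not, because the rule coincides with the arm.

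**The case against.** The strongest reply is that this is loose drafting rather than a difference in care. Both lists are introduced by the word *include*, so neither claims to be complete, and item b does not forbid referral for medication-explained bleeding. If the pointer in item a refers to the Control group section, the unrestricted trigger already applies in both arms. Staff might equally discount medication-explained bleeding among controls. Referral is also not angioplasty: the Background describes referral for an angiogram to look for stenosis, and surveillance patients keep every other trigger as well as monthly flow.

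Part of this stands. The discrepancy may be a slip, and the path from the bleeding rule to an angioplasty has a further clinical step. But an open-ended list can add triggers; it does not remove one that is listed without qualification. Nor does it explain why an exception was written for one arm only. If the difference is a slip, correcting it is uncontroversial. If it is intended, the description of surveillance as flow added to standard care is inaccurate.

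A reader might go further and treat the Transonic check as a second contradiction. The documents do not support that: the check is marked as rare, it uses the device under study, and it plausibly belongs to the strategy being tested. A reader might also take the missing word *low* before Kt/V, or the pressure limits given as examples, as a wider surveillance list. The first reads as a dropped word, and the pressure limits are identical in both arms.

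**Conclusion.** The point holds for one trigger. As written, medication-explained bleeding over 30 minutes is an indication for referral among controls and is left out of the surveillance list, against the stated definition of the surveillance arm. If nurses follow the lists, clinically triggered referral differs by arm for a reason other than flow measurement, and this could affect H0-2. The conclusion assumes that staff apply the text literally and that some of these referrals lead to procedures. The size cannot be computed from the documents and could be negligible.

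Two stronger inferences should not be drawn. One is that the primary comparison of thrombosis is biased; nothing in the documents links referral for medication-explained bleeding to thrombosis. The other is that the trigger must be important because the Background names prolonged bleeding first among the signs of access dysfunction. Bleeding not explained by medication triggers referral in both arms, and the Background says nothing about the subset in dispute.

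**What to change.** Write one list of clinical referral triggers and have both arms refer to it, with the flow thresholds in Surveillance group item a as the only addition. Put the medication exception in the shared list for both arms or delete it; which is clinically right is for the investigators. If the Transonic check before referral for Kt/V or recirculation is meant to be part of the surveillance strategy, describe it as such. State either that the clinical trigger still leads to referral or what a normal result leads to, and amend the description of surveillance as flow added to standard care to match.

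The cost is a wording amendment to two paragraphs, plus a sentence or two if the check is kept. It needs no extra visits, tests or patients.

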H_{0-1} : Patients screened monthly with UDT and followed up with proactive intervention (if clinically indicated) will not have a time to thrombosis that is different than patients receiving physical examination and reactive intervention (if clinically indicated)

H_{0-2} : Patients screened monthly with UDT and followed up with proactive intervention (if clinically indicated) will not have a number of angioplasty procedures that is different than patients receiving physical examination and reactive intervention (if clinically indicated)

H_{0-3} : Patients screened monthly with UDT and followed up with proactive intervention (if clinically indicated) will not have a number of thrombectomy procedures that is different than patients receiving physical examination and reactive intervention (if clinically indicated)

H_{0-4} : Patients screened monthly with UDT and followed up with proactive intervention (if clinically indicated) will not have a rate of tunneled dialysis catheter (TDC) that is different than patients receiving physical examination and reactive intervention (if clinically indicated)

H_{0-5} : Patients screened monthly with UDT and followed up with proactive intervention (if clinically indicated) will not have a rate of non-tunneled dialysis catheter (non-TDC) that is different than patients receiving physical examination and reactive intervention (if clinically indicated)

Sample Size:

$\alpha = 0.05$, $\beta = 0.80$, 2-sided (testing benefit and harm)

Main predictor: Treatment or control; Main outcome: Thrombosis or no—two-sided therefore chi-square for proportions of dichotomous variables was used for sample size calculations.

Treatment versus control estimates of thrombosis (based on Tessitore 2004; Scaffaro 2009, Moist 2003, Robbin 2006, Sands 1999, Ram 2003, Tessitore 2008): 34% in control; 24% in treatment (effect size 30%); 342 per group; loss to f/u (move, transplant, different clinic) 5% = $1/(1-.5)=1.05=359$ (low estimate); loss to mortality 10% a year = 1.11 2x (per [name]) = 443

Variables to be collected at baseline:

age, sex, race (white, black, Asian/Pacific Islander, American Indian/Alaskan Native), ethnicity (Hispanic or not), insurance type (private, Medicaid, Medicare,

Hemodialysis Access Surveillance Evaluation (HASE) Study

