[name] brings over 20 years' experience to the current study. She has the experience and skills to ensure timely completion of all the project milestones, organize communications among investigators, ensure regulatory and IRB compliance, overs study and effectively multi-task the various administrative duties associated with large complex studies. She also contributes to manuscripts for publication and data presentations at scientific meetings.

- **[name] RN (AMC Study Coordinator and Dialysis Center staff)**

[name] has over 16 years' experience in dialysis access and hemodialysis therapy. She is CITI certified and is highly skilled at recruiting, enrolling and retaining participant's in previous studies. She has demonstrated that she can efficiently and effectively coordinate the flow of participants during their study visits to the CRC, reinforce compliance with study interventions, collect and retain data in a well-organized manner, and maintain updated regulatory documentation and case report forms.

Recruitment Methods

Study staff will identify potential subjects from dialysis centers mentioned above. Subjects will be approached for a brief conversation to establish if there is interest in hearing about the study. If the patient is interested, the study coordinator will then present a detailed explanation of the study.

Subjects who meet all of the inclusion criteria ascertained at the screening visit will be enrolled in the study. In order to reach the goal of 450 subjects who complete the protocol, we will screen up to 900 subjects with CKD, allowing for a screening to enrollment ratio of 2:1. Once the target enrollment is complete we will discontinue screening irrespective of whether we have yet to reach 900 subjects.

Study team members who approach patients at centers will be very careful of explaining to potential subjects that research participation is completely voluntary and that their decision whether to participate or not, will have no impact in their medical care. Also, participants will receive a full explanation of the extent of their participation in the study prior to signing the informed consent form.

Hemodialysis Access Surveillance Evaluation (HASE) Study

Number of Subjects

450 Patients.

Confidentiality

Patients' identifying information will be stored in a password-protected, firewall enabled database, only available to approved study staff. The database will be kept for the duration of the study.

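### The sample-size calculation requires 443 patients per group (886 in total), but the trial enrols 450 in total, which gives about 49–65% power instead of 80%.

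*Combined protocol and SAP*

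**What the plan says.** Under Data Management, the Sample Size paragraph sets alpha at 0.05, "2-sided (testing benefit and harm"), and gives 0.80 under the symbol beta, evidently meaning power. It states that "chi-square for proportions of dichotomous variables was used for sample size calculations". The result is "34% in control; 24% in treatment (effect size 30%); 342 per group".

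Two inflation steps follow. The first is "loss to f/u (move, transplant, different clinic) 5"%, a factor of 1.05, which takes 342 to 359. The second is "loss to mortality 10% a year = 1.11 2x (per [name]) = 443", that is, a factor of 1.11 for each of two years.

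Elsewhere the size of the trial is 450. Number of Subjects gives 450 patients. Procedures Involved says "End of study starts as last patient from 450 completes follow-up". Recruitment Methods says "In order to reach the goal of 450 subjects who complete the protocol, we will screen up to 900 subjects with CKD", and describes this as a 2:1 ratio of screening to enrolment.

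**The concern.** The figure of 342 is labelled per group, and the later steps multiply it only by attrition factors. The unit therefore does not change, and 443 is also per group. A whole-trial figure of 450 is about half of the resulting 886. Its closeness to 443 suggests that the per-group number was rounded and used as the total. That explanation is inference; the mismatch does not depend on it.

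Recruitment Methods adds a second inconsistency. It calls 450 the number who complete, yet screening 900 at 2:1 makes 450 the number enrolled.

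The Objectives justify the trial by the small samples and weak power of earlier randomised studies, and mention a growing view that surveillance is futile. A trial with half its required size repeats the fault it was meant to remedy. A null result could then be read as support for futility when the design had a large chance of missing the effect it was planned to find.

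**Working it through.** **Inputs from the Sample Size paragraph.** Control p1 = 0.34; treatment p2 = 0.24; two-sided alpha 0.05 (z = 1.960); power 0.80 (z = 0.842); chi-square for two proportions; loss factor 1.05; mortality factor 1.11 applied twice.

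**Assumption.** Equal arms. Shifts alternate between arms within a clinic (Randomization), but no patient-level ratio is stated.

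**Step 1: reproduce 342.** With mean proportion p = 0.29 and d = 0.10:

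- n = [1.960·√(2p(1−p)) + 0.842·√(p1(1−p1) + p2(1−p2))]² / d²
- n = [1.960 × 0.6417 + 0.842 × 0.6378]² / 0.01 = 322.0 per group
- With continuity correction: n′ = (n/4)·[1 + √(1 + 4/(n·d))]² = 341.7, which rounds up to 342 per group

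The match is exact, so 342 is a per-group size. If 342 were the total (171 per group), power would be 53%, or 48% corrected.

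**Step 2: reproduce 443.**

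- 342 × 1.05 = 359.1, stated as 359
- 359 × 1.11² = 442.3, stated as 443
- Two groups: 2 × 443 = 886 to enrol, so that 2 × 342 = 684 are evaluable
- Planned: 450/886 = 51% of the requirement

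**Step 3: power with 450 in total.** For k per group, power = Φ{[d√k − 1.960·√(2p(1−p))] / √(p1(1−p1) + p2(1−p2))}. The corrected version replaces d by d − 1/k.

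| Reading of 450 | Evaluable per group | Uncorrected | Corrected |
|---|---|---|---|
| Plan's target | 342 | 82.3% | 80.0% |
| All 450 evaluable | 225 | 64.8% | 60.8% |
| 450 enrolled, plan's attrition | 174 | 53.8% | 49.1% |

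The last row uses 450/(1.05 × 1.11²) = 348 evaluable, or 174 per group. Applying the stated losses directly, 225 × 0.95 × 0.81 = 173 per group, gives almost the same power (53.6% and 48.8%).

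**Step 4: effect detectable at 80% power with 174 per group.** Against 34% in control, the treatment rate must be 20.7% (uncorrected) or 20.1% (corrected). That is a relative reduction of 39% or 41%, compared with the stated 30%.

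**Step 5: if 450 means completers.** Enrolment must be 450 × 1.05 × 1.11² = 582.2, so 583. Even then, 450 evaluable patients fall short of 684.

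**Step 6: clustering, for direction only.** Whole shifts are randomised and the calculation contains no design effect. The documents give neither the shift size nor an intracluster correlation. Assuming 10 to 20 patients per shift and a correlation of 0.01 to 0.05, the design effect 1 + (m − 1)·ICC runs from 1.09 to 1.95. Uncorrected power then falls to about 39–61% at 225 per group and 31–50% at 174 per group.

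**The case against.** The contradiction between 443 per group and 450 in total is hard to dispute; the serious objections are to the precision of the power figures and to the remedy.

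- **The range mixes readings and formulas.** If 450 complete, power is 61–65% and the chance of missing the effect is 35–39%. Only on the enrolled reading is that chance close to even. This is right, and the table keeps the readings apart. No reading comes near 80%.
- **The continuity correction is inferred.** The plan says only chi-square. The correction is the version that reproduces 342, which does not show that the planned test will use it. For an uncorrected test the range is 54–65%.
- **Counting only completers is pessimistic.** Patients who clot before dying or leaving still contribute events, and Statistical Analysis also plans Kaplan-Meier and Cox analyses that use partial follow-up. This stands as a reason to treat 49–54% as the low end before clustering. It cannot lift power above the 65% obtained when all 450 are evaluable.
- **Clustering is left out.** A replacement power of 49–54% would itself be too high if presented as what the trial delivers. This also stands. It strengthens the finding and means that any restated figure must be labelled as ignoring clustering, or adjusted under stated assumptions.
- **Rewording does not make the trial adequately powered.** True. Disclosure corrects the claim but does not meet the aim in the Objectives, so the sponsor should make that choice openly.

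**Conclusion.** The concern holds. The plan's own arithmetic, reproduced at both steps, needs 443 per group and 886 in total, while the protocol fixes the whole trial at 450 without justification. The 80% power claim is wrong on every reading of 450: 61–65% if all 450 are evaluable, and 49–54% if 450 are enrolled and the stated attrition applies. These figures rest on roughly equal arms and the plan's rates of 34% and 24%, and they treat patients as independent. Unequal shift sizes would change them slightly; clustering by shift would reduce them. Because the error concerns the primary outcome and the trial's stated rationale, it must be corrected.

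**What to change.** 1. In Sample Size, state that 443 is per group and that the requirement is 886 in total.
2. If 450 in total is kept, replace the 80% claim with one of two statements: the power that 450 delivers (about 49–54% after the stated attrition for 34% versus 24%), or the difference detectable at 80% power (34% versus about 20–21%). Mark either as before clustering, or add a design effect with its assumed shift size and intracluster correlation. If all 450 are to be evaluable, the corresponding power is 61–65% and about 583 must be enrolled.
3. State that a non-significant primary result will be reported as inconclusive, through the confidence interval for the difference, and not as evidence that surveillance is futile.
4. Make Procedures Involved, Recruitment Methods and Number of Subjects agree on whether 450 are enrolled or complete the protocol.
5. In the same edit, correct two minor slips that change no result: 1/(1−.5) should read 1/(1−.05), and the 0.80 given as beta should be given as power.

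The cost is protocol wording and a less favourable stated power. Keeping 450 as the number enrolled needs no extra patients. Restoring 80% power would require enlarging the trial to at least 886, and more once clustering is allowed for.

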Veterans/Military, uninsured), length of time in dialysis (weeks); diabetic (y/d), CAD, PVD, HTN, how long access has been in place (weeks), location (Right/Left, arm/forearm), type of access (AVF or AVG), other clinical variables, button hole, history previous access (Y/N), history of previous catheter (Y/N), length of catheter placement/use (Days)

Variables to be collected monthly:

Monthly questionnaire.

Statistical Analysis:

- **Step 1:** Descriptive analysis to assess similarity of patients between trial arms and to assess representativeness of study participants to hemodialysis patients (generalizability).
- **Step 2:** Descriptive analysis for primary outcome (chi-square) and secondary outcomes (t-test or non-parametric equivalent)
- **Step 3:** Kaplan-Meier Survival Curve (unadjusted)
- **Step 4:** Survival Time Analysis Cox proportional hazards model (adjusted)
- **Step 5:** Multilevel regression with random effects in a mixed regression model to adjust for potential group-level RN, center, city effects. Primary analysis is a dichotomous variable (y/n). Secondary analysis outcomes continuous but may be treated as categorical variables

Covariates for evaluation in the models: individual-level predictors: age, race, sex, insurance, length of time in dialysis (weeks), diabetes (y/n), CVD (y/n), how long access has been in place (weeks), access location, type of access, location of access , length of time in study before thrombosis or mortality (weeks); other significant clinical variables group-level predictors: RN, dialysis center, city

Cross-overs: intervention participants who do not get clinically indicated treatment will be analyzed in two ways--included in treatment arm (intention-to-treat) and excluded (per protocol)

Statistical monitoring: analysis will be conducted 6 months; 12 months; 18 months; and 24 months. If a clear benefit is identified early or if the intervention is unexpectedly harmful, the study will be stopped early.

Risks to Subjects

Risk from Ultrasound Dilution Technique: UDT is a non-invasive procedure that generates no risk to patients undergoing hemodialysis. We do not anticipate any problems as a result of patients undergoing this procedure.

Risk to Privacy: There may be breach of confidentiality regarding protected health information. To minimize the potential risk to privacy all data are de-identified with use of study specific ID numbers only. To ensure that participants' confidentiality is

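### The plan does not say whether the Step 2 chi-square or the Step 5 mixed model decides the primary yes/no thrombosis hypothesis, and the model's covariate set is left open

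*Combined protocol and SAP*

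**What the plan says.** All references are to the combined protocol and SAP.

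- **Primary Hypothesis.** The null is that patients screened monthly "will not have a rate of access thrombosis that is different than patients receiving physical examination and reactive intervention". No test is attached to it.
- **Sample Size.** The main outcome is thrombosis or not, and "chi-square for proportions of dichotomous variables was used for sample size calculations". The two-sided alpha of 0.05 is given here and nowhere else.
- **Statistical Analysis, Step 2.** "Descriptive analysis for primary outcome (chi-square) and secondary outcomes".
- **Steps 3 and 4.** An unadjusted Kaplan-Meier curve and an adjusted Cox model.
- **Step 5.** A multilevel model with random effects for nurse, center and city, followed by: "Primary analysis is a dichotomous variable (y/n". This is the only use of the term primary analysis, and it describes the type of variable.
- **Covariates.** The list is offered for evaluation in the models. It includes the time a patient spends in the study before thrombosis or death, and it ends with "other significant clinical variables group-level predictors: RN, dialysis center, city". No selection rule is given.
- **Secondary Hypotheses.** The first of these, H0-1, concerns time to thrombosis. No analysis step is tied to any hypothesis.
- **Cross-overs.** Intention-to-treat and per-protocol analyses are both planned, and neither is named as primary.

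**The concern.** The endpoint is clear, but the test that decides it is not. The sizing points to an unadjusted chi-square, and the wording of Step 5 points to an adjusted mixed model. They are different analyses. One ignores covariates and group structure. The other depends on which covariates enter, and the plan leaves that open.

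The covariate on time in study adds a further problem. For a patient whose access clots, it is the event time itself. If surveillance delays or prevents thrombosis, adjusting for this variable removes part of the effect under test. The plan permits a model with it and a model without it.

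At stake is whether the primary verdict is settled before the data are seen. The gap also reaches the interim analyses at 6, 12 and 18 months, where the study may stop for clear benefit but no test is named to show it.

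**Working it through.** **1. Which test was the trial sized on?** Inputs from Sample Size: 34% versus 24%, two-sided alpha 0.05, and 0.80 (labelled beta, but it works only as power). The average proportion is 0.29.

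- Uncorrected: n = [1.960 × √(2 × 0.29 × 0.71) + 0.842 × √(0.34 × 0.66 + 0.24 × 0.76)]² / 0.10² = (1.258 + 0.537)² / 0.01 ≈ 322.0, so 323 per group.
- Continuity-corrected: (322.0 / 4) × [1 + √(1 + 4 / (322.0 × 0.10))]² ≈ 341.8, so 342 per group.

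The plan states "34% in control; 24% in treatment (effect size 30%); 342 per group". The corrected formula reproduces 342 exactly. The trial is therefore sized on an unadjusted chi-square for independent patients, the test that Step 2 calls descriptive.

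**2. Which steps compete for the primary?** The primary outcome is yes/no. Step 2 and Step 5 both address it. Steps 3-4 analyze time to event and fit H0-1. The contest is Step 2 against Step 5, with more than one possible version of Step 5.

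**3. Ceiling on the false-positive rate.** Take three tests at 0.05: chi-square, full model, and a model with selected covariates. If they were independent, the chance of at least one false positive would be 1 − 0.95³ = 14.3%. The Bonferroni bound is 15%. These tests share the same data and are strongly correlated, so the real figure is far lower.

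**4. Simulated false-positive rate, no shift effect.** All settings are assumed: 450 independent patients, no treatment effect, ordinary logistic regression standing in for the mixed model, no interim looks. The rate counted is at least one of those three yes/no tests falling below 0.05.

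| Simulation | Result |
|---|---|
| 10 baseline covariates, 6,000 trials per setting, moderate effects | 6.5% |
| Same, effects doubled | 7.2% |
| Separate check at other assumed settings | 6.6-7.7% |

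In another run without a shift effect (five covariates, 1,500 trials), each test alone was near 5%: chi-square 4.7%, full logistic 5.1%, selected-covariate logistic 5.0%.

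**5. Disagreement at 34% versus 24%.** The chi-square and the full adjusted model fell on opposite sides of 0.05 in 7.9% (moderate effects) and 14.7% (doubled) of trials. A check at other settings gave 10-18%. A further check with six assumed covariates split the disagreements by direction:

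| Total | Only adjusted model significant | Only chi-square significant |
|---|---|---|
| 7.5% | 5.3% | 2.1% |
| 14.7% | 11.3% | 3.4% |

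About 5.3 / 7.4 = 72% and 11.3 / 14.7 = 77% of the disagreements are the adjusted model detecting an effect that the chi-square missed.

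**6. Would naming the Step 5 model as written be enough?** Under Randomization, whole shifts within a clinic are allocated together. The Step 5 random effects are nurse, center and city, with no term for shift. Null simulations with an assumed shift effect:

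- Adjusted model with no group-level term, shift SD 0.3: rejects about 7.7%.
- Adjusted model with center as a fixed effect (6 clinics × 6 shifts; nurse and city not modelled), shift SD 0.3 on the logit: 7.8%. At SD 0.5: 11.7%.
- Unadjusted chi-square, shift SD 0.3 on the log hazard: 6.9%.
- t-test on shift-level proportions, same setting: 4.3%.

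A single named test that omits shift is therefore not shown to hold 0.05. Nurse terms might absorb some of the shift effect, but this was not tested.

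**The case against.** The best defense is that the plan can be read sensibly. Step 2 is labelled descriptive and Step 5 carries the words primary analysis, so the mixed model is the primary test. That reading is reasonable, and the fix adopts it. It does not close the gap: the covariates stay open, the sizing still points to the chi-square, and nothing prevents the Step 2 result from being reported as the verdict.

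Four stronger readings are tempting, and the documents do not support them.

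- **Kaplan-Meier and Cox are also rivals for the primary.** A reader might infer this because no step is tied to a hypothesis. But H0-1 is a separate hypothesis on time to thrombosis, and these steps fit it. Step 3 names a curve, not a log-rank test. Simulated rates of 8.1-10.5%, which count log-rank and Cox results as wins on the primary, do not measure this fault.
- **Covariates will be chosen by p-value.** The word significant may mean clinically important, and no p-value rule is written. What stands is that the set is open.
- **Every listed test is set at 0.05.** Alpha appears only under Sample Size. The Statistical Analysis section gives no level for any step.
- **Disagreement in 8-18% of trials is all arbitrariness.** Most of it is the extra power that adjustment brings when the effect is real.

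**Conclusion.** The concern holds in limited form. The plan leaves the choice between chi-square and mixed model unranked, does not fix the covariates, and lists one covariate that should not be in a model of the treatment effect. The inflation of the false-positive rate is modest, to about 6.5-7.7%. This figure rests on assumed covariate effects, independent patients, ordinary logistic regression in place of the mixed model, and no interim looks. The main fault is that the verdict is not pre-specified. It should be corrected, but it does not by itself invalidate the trial. The effect of adjusting for time in study was not quantified.

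**What to change.** State in Step 5 that one test decides the primary hypothesis: the treatment term in the intention-to-treat mixed logistic model, at two-sided 0.05. Specify that the model has:

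- a random effect for the randomized unit (shift within clinic), in addition to the listed group-level effects;
- a covariate set fixed before unblinding and drawn from variables collected at baseline, for example age, sex, diabetes, access type, access location and access age.

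Remove from this model the open-ended clinical variables and the time in study before thrombosis or death. Label the Step 2 chi-square, and any model with other covariates, as supportive and unable to replace the primary result. Assign Steps 3-4 to H0-1. If the sponsor prefers another single test, the same sentence can name it, provided that the test accounts for shift.

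The cost is mainly wording before unblinding, since the example covariates are already on the baseline list. Other covariate sets become sensitivity analyses. The Sample Size text should note that 342 per group came from an unadjusted chi-square that ignores clustering, and so does not describe the power of the named model.
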